PROTOCOL TITLE: Targeted Neuroplasticity after Spinal Cord Injury**PRINCIPAL INVESTIGATOR:**

[name]

Neuromodulation Lab
 Shirley Ryan AbilityLab (22nd floor)
 [name]
 [name]

Site(s) where study will be performed:

Version Date	8/5/2021
Investigational Agent(s) (Drugs or Devices)	
IND / IDE / HDE #	
Indicate Special Population(s)	 Children  Children who are wards of the state  Adults Unable to Consent  Cognitively Impaired Adults  Neonates of Uncertain Viability  Pregnant Women  Prisoners (or other detained/paroled individuals)  Students/Employees N/A
Sample Size	500
Funding Source	Institutional funds/Northwestern University
Indicate the type of consent to be obtained	 Written  Verbal/Waiver of Documentation of Informed Consent  Waiver of HIPAA Authorization  Waiver/Alteration of Consent Process
Site	 Lead Site (For A Multiple Site Research Study)  Data Coordinating Center (DCC)
Research Related Radiation Exposure	 Yes  No
DSMB / DMC / IDMC	 Yes  No

OBJECTIVES:

The purpose of this study is to test a strategy to restore upper and lower-limb motor function in individuals with spinal cord injury (SCI). We have the following two specific aims:

Aim 1. Maximize exercise-mediated recovery of limb muscles by using stimulation induced spinal plasticity. We will study the effect of limb training combined with Spike-Timing Dependent Plasticity (STDP) on motor function recovery. We will test the effect of three groups: (1) stimulation, (2) training +stimulation, and (3) training+sham stimulation. We hypothesize that the ability of training to promote recovery of limb motor function will be enhanced by eliciting STDP in upper and lower-limb. An important strength of this aim is the combination of training and STDP, which aims at enhancing the beneficial effects of motor training by promoting plasticity in the corticospinal pathway (Ellaway et al., 2007; Castel et al., 2009). Training effects on physiological pathways will be explored and correlated with hand/arm motor function and the site and extent of the lesion defined by structural MRI.

Aim 2. Maximize exercise-mediated recovery of limb muscles by using stimulation induced spinal plasticity. STDP has been shown to be effective in enhancing the recovery of residual limb function in humans with chronic incomplete SCI (Urbin et al., 2017). In this aim we will investigate the effect of the combination of extended STDP and training. We hypothesize the ability of training to promote recovery of motor function will be enhanced by eliciting STDP in the corticospinal pathway.

BACKGROUND:

After a SCI, many individuals present deficits in upper-limb and/or lower-limb function. Most SCIs are contusions and ~50% occur at the cervical level causing anatomically incomplete damage and bilaterally functional deficits to lower- and upper-limbs (Kakulas, 1999). Arm and leg function deficits limit daily-life activities, such as reaching and grasping, eating, writing, and walking which decreases the quality of life (Snoek et al., 2004). Regaining arm and leg function is considered the highest priority for improving the quality of life of individuals with SCI (Anderson, 2004).

Rehabilitation strategies in humans with SCI rely on the use of exercise (Harkema et al., 2012; Behrman et al., 2017). Exercise training aims to drive neural networks in an activity-dependent manner to elicit plasticity and facilitate functionally relevant muscle activity below the level of injury (Knikou, 2010). Studies using animals (Courtine et al., 2009; Hill et al., 2009; McPherson et al., 2015) and humans (Rejc et al., 2017; Gad et al., 2018; Gill et al., 2018) agree that physiological and functional effects of exercise can be augmented by the use of neural stimulation, which is thought to increase the likelihood of activating spared neural pathways. Even though these approaches have facilitated exercise-mediated recovery, the overall effects remain limited. Clearly, there is a need to develop interventions that can more effectively engage spared neural connections to further improve functional recovery due to rehabilitative exercise in humans with SCI.

Evidence has shown that corticospinal transmission can be enhanced by precisely timing pairs of presynaptic and postsynaptic action potentials arriving at the spinal cord (Taylor & Martin, 2009),

which can enhance voluntary motor output in humans with (Bunday and Perez, 2012) and without (Taylor & Martin 2009) SCI. Evidence has shown that the activity in upper-limb muscles can be enhanced by activations of the lower limb (Zhou et al., 2017). Therefore a strategy that combine upper and lower limb stimulation and activity might be more effective to enhance upper limb function. In this protocol, we will test the effect of training combined with stimulation to facilitate upper and lower limb function.

How STDP and training might contribute to recovery of upper-limb and lower-limb function: The physiological basis for these protocols comes from animal studies showing that an increase or decrease in synaptic strength can be elicited by repeated pairs of presynaptic and postsynaptic action potentials that are precisely timed with respect to each other (Bi & Poo, 1998; Dan & Poo, 1998; Bi & Poo, 2001). If antidromic stimulation of a postsynaptic cell is paired with timed orthodromic stimulation of a presynaptic cell, bidirectional plasticity can be induced (Bi & Poo, 1998; Markram et al., 1997). In humans, corticospinal neurons can be activated by transcranial magnetic stimulation (TMS), and antidromic action potentials can be elicited in sensorimotor cortex and motoneurons by peripheral nerve/ spinal cord stimulation. STDP has been used successfully to precisely pair pulses to arrive at the spinal cord (Taylor & Martin, 2009). How to strengthen synaptic plasticity in corticospinal connections targeting the spinal cord (spinal synapses) of upper-limb and lower-limb muscles after SCI combined with training and its effect on voluntary output, remains unknown and will be investigated in this study.

STUDY ENDPOINTS:

The primary outcome measure utilized in this part of study is the Graded Redefined Assessment of Strength, Sensibility and Prehension (GRASSP see below). GRASSP is an extensive and validated impairment and functional measure which is able to detect subtle neurologic changes in individuals with spinal cord injury. Specifically, it evaluates the domains of sensation, strength, quality of different grip patterns and the ability to complete a variety of functional tasks.

The primary outcome measure utilized in this part of study the 10-meter Walk test. In the group receiving lower-limb exercises, we will use the 10-meter walk test to assess walking speed in meters per second. The same percentage of body-weight support will be used during pre- and post-assessments. A stopwatch will be used to measure the time to execute the task. The 10-meter walk will be repeated 3 times and the average will be used.

Participants may complete the following secondary endpoint measurements before and after the STDP protocol as outlined below.

A). MEPs: Transcranial magnetic stimuli (TMS) will be delivered from a Magstim 200 stimulator (Magstim Company) through either a figure-of-eight coil (loop diameter, 7 cm) or a double-cone coil (used for the tibialis anterior muscle) with a monophasic current waveform. TMS will be delivered to

the optimal scalp position for activation of dominant muscles in controls and the furthest muscle with residual connectivity below the level of injury in individuals with SCI. The optimal scalp position will be determined by moving the coil in small steps along the hand/arm/leg representation of the primary motor cortex to find the region where the largest MEP can be evoked with the minimum intensity in the targeted muscle(s). The muscles to be activated will be the first dorsal interosseous, abductor pollicis brevis, flexor and extensor carpis radialis, biceps and triceps brachii, deltoid, quadriceps femoris, hamstrings, tibialis anterior and soleus. Measurements: resting (minimum intensity required to induce MEPs greater than 50 μ V in 5/10 consecutive trials at rest), and active (minimum intensity able to evoke an MEP bigger than 200 μ V in 5/10 consecutive trials during 5-10% of MVC) motor threshold. Thirty MEPs will be average in each condition.

B). CMEPs: Supramaximal electrical stimulation will be administered posterior to the mastoid process or thoracic spine to elicit motor evoked potentials to upper- and lower-limb muscles.

C). Motoneuronal excitability (reflected by F-wave persistence and amplitude): Using supramaximum stimulus intensity (120% of the maximal motor response, M-max; 0.2 ms duration, 20 trials (88)) to the ulnar nerve at the wrist for the first dorsal interosseous, median nerve at the wrist for abductor pollicis brevis, brachial plexus at the erb's point for the deltoid and biceps brachii, femoral nerve for quadriceps, and common peroneal nerve under the head of the fibula for the tibialis anterior and posterior tibial nerve behind the knee joint for the soleus. We will quantify latency, peak-to-peak amplitude of each F-wave, and F-wave persistence (number of F-waves present on each set).

D) H-reflex: Quadriceps femoris H-reflex and M-max: Participants are comfortably seated in an armchair. Percutaneous electrical stimulation of the femoral nerve will be delivered (using 1 ms rectangular electrical stimulus, DS7AH, Digitimer Ltd.) through a cathode (10-mm diameter Ag-AgCl electrode) placed in the femoral triangle and an anode (Ag-AgCl plaque) placed over the posterior aspect of the thigh. Stimulus intensities will be increased in steps of 0.05 mA, starting below H-reflex threshold and increasing up to measure the H-max and M-max at rest (0.25 Hz). The H-max and Mmax will be measured as peak-to-peak amplitude of the non-rectified response in control subjects and both legs of individuals with and without spasticity as determined by the MAS. MAS this clinical scale will be used by measuring resistance encountered during manual passive muscle stretching using a six-point ordinal scale (0=no increase in tone, 1+1=slight increase in tone with a catch and release or minimal resistance at the end or less than half of the range of movement, respectively, 2=more marked increased tone through most of the range of movement but affected parts easily moved, 3=considerable increase in tone and passive movement difficultly, and 4=affected parts rigid; Bohannon and Smith, 1987). **Tibialis anterior H-reflex and M-max:** Participants will be comfortably seated in an armchair. Percutaneous electrical stimulation of the common peroneal nerve will be delivered (using 1 ms rectangular electrical stimulus, DS7AH, Digitimer Ltd.). Stimulus intensities will be increased in steps of 0.05 mA, starting below H-reflex threshold and increasing up to measure the H-max and M-max at rest (0.25 Hz). The H-max and M-max will be measured as peak-to-peak

amplitude of the non-rectified response in control subjects and both legs of individuals with and without spasticity as determined by the MAS. Soleus H-reflex and M-max: Participants will be comfortably seated in an armchair. Percutaneous electrical stimulation of the posterior tibial nerve will be delivered (using 1 ms rectangular electrical stimulus, DS7AH, Digitimer) through a cathode (10mm diameter Ag-AgCl electrode) placed in the popliteal fossa over the posterior tibial nerve and an anode (Ag-AgCl plaque) placed over superior to the patella. Stimulus intensities will be increased in steps of 0.05 mA, starting below H-reflex threshold and increasing up to measure the H-max and Mmax at rest (0.25 Hz). The H-max and M-max will be measured as peak-to-peak amplitude of the non-rectified response in control subjects and both legs of individuals with and without spasticity as determined by the MAS.

E) EMG and force voluntary output: Individuals will perform a maximum voluntary contraction (MVC) of the targeted muscles (deltoid, biceps brachii, first dorsal interosseous, abductor pollicis brevis, quadriceps femoris, tibialis anterior and/or soleus) through surface electrodes secured to the skin over the belly of each muscle (Ag-AgCl, 10 mm diameter). The signals will be amplified, filtered (20–1000 Hz), and sampled at 10 kHz for offline analysis.

F) Nine Hole Peg Test (9HPT): This test measures finger dexterity. The board is placed at the participant's midline, with the container holding the pegs facing toward the hand being tested. Nine small pegs are placed in a container and subjects are instructed to pick up each of the pegs and put them back as fast and accurately as possible. The time to complete the task is measured in seconds.

G). Jebsen Taylor Test (JTT): This test measures hand function. The time in seconds to complete subcomponents of the JTT will be measured for both hands.

H) Chedoke Arm and Hand inventory (CAHAI): This test measures upper-limb motor recovery. Quantitative scale with 13 items (each item is given a score: 1 to 7).

I) Electrical Perceptual Threshold (EPT): This test provides a quantitative measure of sensory function by using small pulses of electricity on the surface of the skin and will be used to evaluate sensory threshold in the hands/arms and legs.

J) Kinematics: These will be measured during self-paced and fast grasping or walking movements recorded by OptiTrack V100 cameras (120 Hz) and by Opti Track, V120: Trio camera, NaturalPoint, Inc., with cameras respectively for the locomotor training. Subjects will be seated and grasp with the less affected (participants) and dominant (controls) arm. Cameras will be positioned in front/sides of subjects with markers on the tip of the thumb and index finger, inner side of the wrist, lateral side of the elbow and shoulder joints. Variables: 1) Movement onset (MO): time between the GO signal and start of forward arm velocity. 2) Total movement duration (MD): time between MO and grasp (Gr=time when index and thumb contact target). MD will be broken in

time to reach maximum velocity (MV), maximum hand aperture (MA), and the first finger contact (FC), and Gr.

K) Startle: We will test the StartReact response to assess contributions from the reticulospinal tract. Participants will be asked to observe a red LED located ~1 m in front of them. When the LED is illuminated, individuals will be asked to perform as fast as possible isometric muscle contractions. In some trials, the LED will be presented with a quiet (<95 dB; 50 ms) or a startling (SAS, >115 dB; 50 ms) acoustic stimulus. We will measure: (a) visual reaction time (defined as the onset of the EMG burst in the contracted muscle after the LED), (b) auditory reaction time (time delay between the presentation of the quiet acoustic stimulus and the onset of the EMG response), and (c) visual+startle reaction time (time between the SAS and the EMG onset).

L) Pendulum Test: As part of the physical exam, we will use the pendulum test to measure muscle tone at the knee by using gravity to provoke muscle stretch reflexes during passive swinging of the lower limb.

M) Portable Spasticity Assessment Device (PSAD): The PSAD combine biomechanical and electrophysiological measurements for an objective quantification of active and passive component of muscle stiffness (Lorentzen et al., 2017). The device functions as a dynamometer integrating measurement of force, joint movement, and reflex-mediated muscle activity.

N) Toronto Rehabilitation Institute-Hand Function Test (TRI-HFT): This exam measures gross motor function frequently used to manipulate objects that participants may encounter in their daily lives. The first part of the test evaluates manual hand dexterity through the ability to use lateral/pulp pinch and palmar grasp to manipulate common objects in three different gravity-related positions: against gravity (supination), toward gravity (pronation), and in a gravity-eliminated plane (mid-prone position). To test the palmar grasp, participants are presented with a: mug, book, soda can, isosceles triangular sponge, and wireless telephone. To test lateral pinch and precision grip, participants are presented with a: paper sheet, Ziploc bag filled with five golf balls, dice, credit card, and pencil. The second part of the test measures the strength of their lateral/pulp pinch and palmar grasp. Participants are presented with nine rectangular blocks, instrumented cylinder, credit card attached to a dynamometer and wooden bar used to measure the torque generated by palmar grasp, the force that the pinch (lateral or pulp) grasp could resist, and the eccentric load that the palmar grasp could sustain. There is no time limit within which the task must be performed. The scoring system is designed to emphasize the type of grasp used to accomplish the task: an active (i.e. ability to develop active finger) or passive (i.e. positioning of the proximal joints) grasp (Kapadia et al., 2012).

O) Neuromechanical hand testing: This exam will measure stretch reflexes flexor and extensor carpi radialis and first dorsal interosseous using a previously described method (Kamper et al., 2001). Stretch reflexes will be elicited by rotation of the wrist joint for flexor and extensor carpi

radialis, and by rotation of the metacarpophalangeal joint for first dorsal interosseous. The arm will be positioned along the trunk, with the elbow flexed at 90° and secured to the device. The wrist and metacarpophalangeal joint will be aligned with the forearm in a neutral position and secured to the motor shaft through a jig such that rotation of the shaft produced rotation of the targeted joint. Rotation will be performed from the maximal joint flexion/extension position. Ten trials will be performed with a few minutes between trials to minimize effects of repeated stretching on subsequent responses.

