All participants will exercise immediately after the stimulation paradigm. Upper-limb exercises will involve gross grasping, fine grasping, and hand cycle using an arm ergometer. During gross grasping, subjects will be asked to reach and grasp cylinders, blocks, cups and lids randomly presented on a table located in front of them at a height of ~20 cm. Then, subjects will be asked to reach and grasp the object to put it back on the table. These sets of movements will be repeated 20 times for each object with breaks as needed. During fine grasping, participants will perform similar movements but they will be asked to reach and grasp smaller objects (peg, bead, pinch pin, cube). During hand cycle, the arm ergometer will be used for 15 minutes and grasping gloves will be used as needed. Movements will be passive, active-assisted, or active depending on participant's ability to perform tasks. In addition, training will consist of grasping with the thumb and index finger targets of different diameters (1, 2.5, and 6 cm) in a vertical board (36x30") positioned in front of them. The board will contain 6 panels (12x15") which will light up individually by a computer cue. Each panel will have three LED lights to indicate grip strength to be exerted (red=30% MVC, blue=20% MVC, yellow=5% MVC). A reflective line in each target will identify the place to grasp, which will be modified to increase task difficulty. Force transducers will run along the sides of each target to communicate with LEDs. Kinematics and EMG signals will be acquired through surface electrodes. Subjects will be instructed to grasp the object between index finger and thumb as fast and accurately as possible holding the final posture for 3 s until the light disappear. 300 trials will be completed.

Lower Limb Training

All participants exercised immediately after STDP or sham-STDP. Lower-limb exercises will involve over-ground walking, treadmill walking, and stair climbing training. During locomotor training, subjects will use a body-weight support system with ~0-70% of body weight support. During treadmill training, subjects will walk at a speed of 0.1-0.3 m/s for 10 minutes using the body-weight support system.

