If eligible, participants will be asked to complete pre, post, and follow-up assessment sessions in addition to the training sessions. Each assessment will require 2-5 sessions. Participants will complete up to 135 training sessions with a maximum of 360 paired pulses of stimulation and a small cohort of participants (n=10) will complete up to 270 training sessions with a maximum of 720 paired pulse of stimulation (up to 4 times per day). This will be determined based on preliminary data. In Aim 1, participants will be tested before and after at least 10 training sessions with single site stimulation. In Aim 2, participants will be tested before and after at least 40 training sessions with multisite stimulation. If a training session is not completed or missed participants will be asked to recover that session in a timely manner.

AIM 1: Randomized controlled design

Pre-assessment: 1. Physiology 2. Kinematics 3. Function	Stimulation Training + stimulation Training + sham stimulation	Post-assessment: 1. Physiology 2. Kinematics 3. Function	Follow-up assessment: 1. Physiology 2. Kinematics 3. Function
--	--	---	--

AIM 2:

Pre-assessment: 1. Physiology 2. Kinematics 3. Function	Training + stimulation	Post-assessment: 1. Physiology 2. Kinematics 3. Function	Follow-up assessment: 1. Physiology 2. Kinematics 3. Function
--	------------------------	---	--

We anticipate that each participant will take about 2-10 months to complete the study procedures/testing. Follow-up assessments will be done 1-9 months after completion of protocol, one follow-up in the first 3 months and the last follow-up in the 4-9 months following the last completed session. We will evaluate the subject's ability to move their hands, arms, legs, feet and/or toes using the different physiological and functional tests as mentioned above. TMS measurements, CMEPS and EMG recordings may also be done at these follow-up assessments.

INCLUSION AND EXCLUSION CRITERIA:

We anticipate the screening of 500 subjects across the two aims (60 subjects for Aim 1, and 40 for Aim 2) who have incomplete SCI at the cervical/thoracic/lumbar level (C2-L2). This number accounts for an attrition rate of 50%. To account for screen failures we would like to ask for a total of 200 subjects.

- Inclusion criteria for SCI subjects:
 - (1) Male and females between ages 18-85 years
 - (2) SCI at least 4 weeks post injury
 - (3) Spinal Cord injury at or above L2
 - (4) ASIA A,B,C, or D, complete or incomplete

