Aim 1: Repeated-measures ANOVA and Tukey post hoc analysis will determine effects of GROUP (stimulation, training+stimulation, and training+sham), TIME (before, immediately after, and follow-ups around 3 and 6 months post intervention) on physiological and behavioral outcomes. For alpha (type I error) of 0.05 and 1-beta (power) of 0.8, 45 SCI participants (15/group) will be included.

Aim 2: Repeated-measures ANOVA and Tukey post hoc analysis will determine effects training stimulation, TIME (before, immediately after, and follow-ups around 9 months post intervention) on physiological and behavioral outcomes. For alpha (type I error) of 0.05 and 1-beta (power) of 0.8, 11 SCI participants will be included.

Audio/Video Taping:

We plan to audio and video taping some parts of the experimental session, upon subject consent (optional in the consent form). Recordings will be only of the experimental activities described in the protocol. The subjects' identity will be hidden if subjects do not explicit consent to be recognized from the video or audio. The audio and video records will be stored in a password-protected file on a USB drive in a locked cabinet in the PI's office at the Rehabilitation Institute of Chicago.

The audio and video records will be used only for:

- a) Medical or scientific publications;
- b) Presentation at conferences;

The audio and video records will be destroyed after the time period chosen in the consent form.

This study does not involve any other risk to the subject, beyond some sense of effort and mild fatigue. Fatigue will be assessed based on the subjects' verbal report. They will be explicitly invited to interrupt the experiment if they experience fatigue. All studies will be carried out in the hospital environment where medical care is immediately available if needed.

POTENTIAL BENEFITS TO PARTICIPANTS:

Participation in the experiment may result in no direct improvement or, in the rare and unanticipated event, worsening of the subject's condition, including prolonged recovery time.

DATA MANAGEMENT AND CONFIDENTIALITY:

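### Aim 2 hypothesises that STDP adds to training, but the plan shows one arm and names no comparator, so its TIME effect cannot test that hypothesis

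*Combined protocol and SAP*

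**What the plan says.** **Objectives, Aim 2.** The aim is introduced by "In this aim we will investigate the effect of the combination of extended STDP and training". The hypothesis follows at once: "We hypothesize the ability of training to promote recovery of motor function will be enhanced by eliciting STDP in the corticospinal pathway". The Aim 1 hypothesis is nearly the same, that the effect of training "will be enhanced by eliciting STDP in upper and lower-limb", and Aim 1 has a training+sham group.

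**Study Timeline.** The first diagram is headed "AIM 1: Randomized controlled design" and lists three arms. The Aim 2 diagram has no design label and one cell, training plus stimulation, between pre- and post-assessment. Aim 1 participants are tested around at least 10 single-site sessions, and Aim 2 participants around at least 40 multisite sessions.

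**Statistical Analysis.** Aim 1 examines "effects of GROUP (stimulation, training+stimulation, and training+sham), TIME". For Aim 2 the sentence is "Repeated-measures ANOVA and Tukey post hoc analysis will determine effects training stimulation, TIME". It gives no groups or levels, and the paragraph ends with alpha 0.05, power 0.8 and "11 SCI participants will be included".

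**Lower Limb Training.** "All participants exercised immediately after STDP or sham-STDP". The sentence does not say which aim it describes.

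**Inclusion and Exclusion Criteria.** Entry is allowed from 4 weeks after injury. The ability criterion is grip or wrist function for Aim 1, and dorsiflexion and hip flexion for Aim 2. Forty subjects are listed for Aim 2, with 50% attrition.

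**The concern.** To say that STDP enhances the effect of training is to make a claim about a difference: recovery with training and STDP, minus recovery with training and no active STDP. The documented Aim 2 observes only the first term. Any change from baseline combines the effect of STDP with the effects of training and repeated testing. In participants enrolled as early as 4 weeks after injury it may also include natural recovery.

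The risk lies in interpretation. Because the hypothesis is worded as enhancement and carries an alpha and a power, a significant TIME effect would naturally be reported as evidence that STDP added to training. It would show only that participants changed.

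If a sham arm was in fact meant, the problem is different: the diagram, the analysis and the sample size all omit it.

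**Working it through.** **1. Does the plan contain the contrast?**

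| Element | Aim 1 | Aim 2 |
|---|---|---|
| Hypothesis | STDP enhances training | STDP enhances training |
| Arms in diagram | stimulation; training+stimulation; training+sham | training+stimulation |
| Design label | randomized controlled | none |
| Analysis factors | GROUP (3 levels), TIME | garbled phrase, then TIME; no levels |
| Sessions and sites | at least 10, single-site | at least 40, multisite |
| Ability criterion | grip or wrist | dorsiflexion and hip flexor |

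No section names a historical control, a crossover period or the Aim 1 sham group as the Aim 2 comparator. The last two rows show that the Aim 1 sham group would not be like-for-like in any case.

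**2. The plan's own figure.** The n = 11 cannot be reproduced, because no effect size, SD, correlation or sidedness is given. Everything below is therefore in SD of the change score and assumes a two-sided 0.05 level.

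Using a paired before/after approximation, power comes from a noncentral t with n − 1 df and noncentrality d√n. At n = 11, 80% power requires d = 0.94 (one-sided: 0.81). As a one-group repeated-measures ANOVA with 3 or 4 visits and an assumed correlation of 0.3 to 0.7, the detectable f is 0.29 to 0.49. Eleven is thus a plausible size for a one-group test of a large change.

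**3. What one arm can deliver.** The 95% CI half-width for mean change is t(0.975, n − 1)/√n:
- n = 11 (stated): 2.228/3.317 = 0.67 SD
- n = 20 (40 × 0.5, if 40 is before attrition): 2.093/4.472 = 0.47 SD
- n = 40 (if 40 is already net of attrition): 2.023/6.325 = 0.32 SD

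More participants sharpen this estimate but do not isolate STDP.

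**4. How a TIME effect can mislead.** Suppose STDP adds nothing and training alone produces an assumed change of 0.3, 0.5 or 0.8 SD. The before/after test at n = 11 is then significant 15%, 32% or 67% of the time.

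**5. If a sham arm was meant.** For a two-sample t-test the noncentrality is d√(n₁n₂/(n₁+n₂)), with n₁ + n₂ − 2 df:
- 11 split 5 and 6: √(30/11) = 1.651. A difference of 0.94 SD has 28% power; 80% power needs 1.91 SD.
- 10 per arm (40 × 0.5 / 2): 80% power needs 1.32 SD.
- 20 per arm (40 / 2): 80% power needs 0.91 SD.

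**The case against.** The best defence is that the enhancement question already has a home in Aim 1, which has randomization, a training+sham group and a GROUP factor. The introductory sentence of Aim 2 asks only about the combination, which fits one arm, the diagram and a TIME analysis. On that view one sentence overclaims, and a one-arm study of an extended regimen is a legitimate choice. This is fair as far as it goes: one arm can describe the combination, and the repair may be only a change of wording. But the hypothesis is stated for Aim 2 itself, with its own alpha and power, and Aim 1 tests a different regimen. The wording decides what Aim 2 may conclude.

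A second objection is that Aim 2 may have a sham arm after all. Its ability criterion is lower-limb, which links the lower-limb sham sentence to Aim 2 at least as naturally as to Aim 1, and the intervention section provides sham for up to 720 stimuli. The analysis sentence is garbled and may have lost a factor, and the diagrams were read from PDF tables. Against this, the Aim 1 diagram came through with all three arms, and the Aim 1 hypothesis also covers the lower limb. The intention remains unsettled, which is itself a reason to reconcile the sections. The later remark in Lower Limb Training that locomotor training follows the STDP protocol does not decide it, because the intervention section uses that name as a heading over both active and sham stimulation.

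Third, the power figures for a split of 11 are hypothetical: nothing proposes such a split, and no source equates the STDP-minus-sham difference with 0.94 SD. That is correct. They show only that n = 11 does not carry over to a two-arm comparison; the defect does not depend on them.

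**Conclusion.** The concern holds. As documented, Aim 2 states a comparative hypothesis, shows a single arm and names no comparator, and nothing elsewhere supplies one. A TIME effect cannot test whether STDP adds to training, at any sample size. The contribution of STDP is not estimable; the mean change is, to within ±0.67 SD of change at n = 11.

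Confidence is high that the sections do not agree and that the hypothesis is untestable as written. Whether the authors intended a sham arm cannot be determined from the documents. The numerical results assume two-sided 0.05 tests on a single change score, because the plan gives no SD, effect size or correlation. The figures at n = 20 and n = 40 also reflect uncertainty over whether the 40 listed for Aim 2 already allows for the 50% attrition.

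**What to change.** First, state whether Aim 2 has a sham arm and which aim the sham sentence under Lower Limb Training describes. Then bring Objectives, Lower Limb Training, the Study Timeline diagram and Statistical Analysis into line.

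**If there is no sham arm:**
- Restate the Aim 2 hypothesis as change from baseline under training plus extended multisite STDP.
- Name TIME as the only factor and report mean change with its 95% confidence interval.
- State that Aim 2 does not attribute change to STDP, and that enhancement is tested in Aim 1 (training+stimulation against training+sham) for the Aim 1 regimen only.

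This is a wording amendment with no added participants or visits. The price is a weaker Aim 2 claim.

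**If there is a sham arm:**
- Add it to the Aim 2 diagram.
- Add a GROUP by TIME comparison to the analysis.
- Justify a sample size for that comparison, rather than carrying over n = 11 and 80% power.

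With a 1:1 split, the 40 listed for Aim 2 give 80% power for a difference of about 1.32 SD (10 per arm after 50% loss) or 0.91 SD (20 per arm if 40 is net of attrition). Smaller differences need more participants: under the same assumptions, a difference of 0.8 SD needs 26 per arm and 0.5 SD needs 64 per arm, before attrition.
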